Treatment efficacy of Proxalutamide relative to placebo arm as assessed by the COVID- 19 ordinal scale (defined in Section 5.1) [Time Frame: Day 28]	A clear cut-off point was used in the COVID-19 scale (scores 1 and 2) so that we were able to measure the effect size recovery ratio [time frame: 28 days].	All scores at Day 28 are informative and is better presented in a graph. As reported for the primary outcome, we clarified a measure of effect within this secondary outcome measure.
Time to recovery [Time Frame: Day 1 through Day 28] Recovery is defined as the first day on which the subject satisfies one of the following two categories from the ordinal scale.1): 2) Not hospitalized, limitation on activities and/or requiring home oxygen; 1) Not hospitalized, no limitations on activities.	Name changed to post-randomization time to recover/alive hospital discharge [time frame: day 1 to day 28] in median days (interquartile range). Recovery was defined as the first day on which the subject reached scores 1 and 2 in the COVID-19 ordinal scale.	We needed to be more specific in this outcome to make it clearer and reproducible.
Proportion of death [Time Frame: Day 1 through Day 28] Defined as the number of subjects who have died in each arm divided by the numbers of subjects randomized to the treatment arm	Name changed to 28-day all-cause mortality rate . The proportion of patients who reached score 8 in the 19-COVID ordinal scale after randomization. [Time frame: 28 days]	The outcome is still the same described in the statistical plan of the final protocol, however we just clarified that it refers to all-cause mortality. All-cause mortality is a more stringent measure, and therefore this change goes against the direction of the bias. Although mortality at 14 days could be contemplated in the original Primary outcome (score 8), we decided to analyze mortality at 28 days only, which is more stringent and reflects the intention-to-treat.
Duration of new oxygen use [Time Frame: Day 1 through Day 28]	Excluded	This outcome measure was not adequately reported by the hospital sites, and therefore we have not included it in the final statistical plan.
Proportion of subjects testing positive for SARS-CoV-2 [Time Frame: Day 14]	Excluded	This outcome also needed to be abandoned because we lacked financial resources to test all patients again for SARS-CoV-2 at day 14.

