--	--	-------------------------------------------------------------------------------------------------------------------------------------------------------------------------------------------------------------------------------------------------------------------------------------------------------------------------------------------------------------------------------------------------------------------------------------------------------------------------------------------------------------------------------------------------------------------------------------------------------------------------------------------------------------------------------------------------------------------------------------------------------------------------------------------------------------------------------------------------------------------------------------------------------------------------

3. General principles

As proposed in the final protocol	Done in the final statistical Plan	Rationale
Continuous variables will be expressed as median (interquartile range [IQR]) and categorical variables will be expressed as a number	Continuous variables were expressed as median (IQR) and categorical variables were expressed as a number and in a risk percentage.	Expression of the categorical variables only as a number is not sufficient to allow for calculation of risk ratios. Then, absolute risk ratios were calculated for primary (14-day Overall Recovery rate) and secondary outcomes (28-day recovery rate and 28-day all-cause mortality)
95% confidence intervals will be calculated for the primary outcome	95% confidence intervals will be calculated for the primary outcome, secondary outcomes and subgroup analysis.	All secondary outcomes expressed in ratios were reported along with the 95% confidence interval to allow for a better understanding of the effect sizes.
Group comparisons will be analyzed by the Wilcoxon rank sum test or χ^2 test	For all categorial effect sizes, hypothesis testing was performed with the χ^2 test, including risk ratios. 95% Confidence intervals were reported in results tables, for the primary endpoint Overall Recovery Ratio), along with the P value. For the Adverse AE table, P-values were included. Other outcomes described as median and IQR were compared with the Wilcoxon rank sum test.	The primary hypothesis testing previously stated was maintained. However, we explained in which cases the different tests were applied to increase transparency.

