Differences between rates of clinical improvement will be calculated using unadjusted ordinal logistic regression or Cox proportional hazard models	We used Kaplan-Meier's survivor function for estimates of proportion surviving, and failure function for estimates of alive hospital discharges. Cox proportional hazards model was kept only to calculate hazard ratio (HR) for death and its 95% confidence interval (CI). Graphical assessment and Kaplan-Meier versus predicted survival showed that of the proportional-hazards assumption has not been violated	For better demonstration of the 95% CI and timeline of the evolution of the outcomes in figures. For measure of effect, as stated in the Primary and Secondary outcomes, we adopted relative risk (or Risk Ratio) for easier understanding.
Statistical analyses will be conducted using XLSTAT version 2020.5.1 (Addinsoft, Inc.)	Statistical analysis was conducted using Stata/SE version 16.1 for Mac (StataCorp LLC, College Station, TX, USA).	Preference of the team performing statistical analysis

4. Statistical hypothesis

As proposed in the final protocol	Done in the final statistical Plan	Rationale

The primary endpoint is the distribution of clinical assessments on the COVID-19 ordinal scale at day 14. The primary outcome will be analyzed using the Wilcoxon rank sum test.
	
The primary efficacy endpoint was described as the overall 14-day recovery ratio. This effect measure was obtained after dichotomization of the COVID-19 ordinal scale for scores 2 and 1, representing patients that were discharged from hospital.
	
Although the distribution is still presented graphically, and tested for statistical significance, a clear cut-off point in the COVID-19 ordinal scale was used to obtain the Overall Recovery Ratio. Recovery ratio is a clinically meaningful effect measure.

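### Time to alive discharge has no rule for deaths or subjects still in hospital at Day 28; ordinary use of the named Kaplan-Meier and Wilcoxon methods would misstate it

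*Combined protocol and SAP*

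**What the plan says.** The final statistical plan (the table of changes that follows the protocol) settles this outcome in several rows.

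- Section 2, Secondary Outcome Measures, names the outcome "post-randomization time to recover/alive hospital discharge [time frame: day 1 to day 28] in median days (interquartile range" in brackets. It adds: "Recovery was defined as the first day on which the subject reached scores 1 and 2 in the COVID-19 ordinal scale".
- Section 3, General principles, on estimation: Kaplan-Meier is used, with the survivor function for survival and the "failure function for estimates of alive hospital discharges".
- The same section, on the comparison of arms: "Other outcomes described as median and IQR were compared with the Wilcoxon rank sum test".
- The same section, on modelling: "Cox proportional hazards model was kept only to calculate hazard ratio (HR) for death". No hazard model for discharge remains.
- Section 5, Primary analysis efficacy, says that the intention-to-treat approach was followed and that missing data were reported.

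Death is a separate secondary outcome, the "28-day all-cause mortality rate". Neither the protocol nor the final plan names a competing-risk estimator, says when deaths are censored in the discharge analysis, or gives a rank or value to a subject who is never discharged.

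**The concern.** A subject who dies in hospital can never be discharged alive, so death is a competing event, not a loss to follow-up. The ordinary Kaplan-Meier failure function (one minus the Kaplan-Meier estimate, 1-KM) censors at the day of death. It then acts as though the dead would later have gone home at the survivors' rate, and so overstates the proportion discharged.

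The Wilcoxon comparison has a related gap. A subject who dies before discharge, or is still in hospital at Day 28, has no first day at score 1 or 2. Unless a rule supplies a value, the test covers discharged subjects only. That group is selected by an outcome that treatment may affect, and restricting to it would be at odds with the intention-to-treat statement.

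Death matters in this trial. Mortality is a named outcome with its own hazard ratio, and inclusion extends to score 6 (non-invasive ventilation or high-flow oxygen; protocol 4.1 and 5.1).

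**Working it through.** **No planned figure to reproduce.** The documents give no expected discharge curve, median time or mortality for this outcome.

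**Inputs from the documents.** Placebo recovery is 39% at 14 days (final plan section 6, from the 61% still in hospital at day 15 in protocol 7.2). The restated effect is 14 points, so 39% + 14 = 53% in the active arm. The total is about 600 subjects, or 300 per arm.

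**Assumptions.** 28-day mortality before discharge from 5% to 30%, constant daily hazards, and no other censoring before Day 28.

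**Formulas.** Let r be the daily hazard of alive discharge and d that of death.

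- True proportion discharged alive by day t: F(t) = r/(r+d) × [1 − exp(−(r+d)t)]
- Proportion dead by day t: d/(r+d) × [1 − exp(−(r+d)t)]
- 1-KM with deaths censored at death: 1 − exp(−rt)

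**Step 1: one arm.** Solve for r and d so that F(14) = 0.39 and Day-28 mortality equals the assumed value. At 30% mortality, r = 0.0428 and d = 0.0236. Then F(28) = (0.0428/0.0664) × (1 − exp(−1.859)) = 0.645 × 0.844 = 54.4%. The failure function reads 1 − exp(−1.198) = 69.8%.

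| Assumed mortality | r | d | True F(28) | 1-KM at Day 28 | Overstatement (points) | Median from 1-KM | Median from true F | Median, discharged only |
|---|---|---|---|---|---|---|---|---|
| 5% | 0.0362 | 0.0029 | 61.6% | 63.7% | 2.1 | 19.2 d | 19.9 d | 10.3 d |
| 10% | 0.0372 | 0.0062 | 60.3% | 64.7% | 4.4 | 18.7 d | 20.2 d | 10.0 d |
| 20% | 0.0395 | 0.0137 | 57.5% | 66.9% | 9.4 | 17.5 d | 21.0 d | 9.2 d |
| 30% | 0.0428 | 0.0236 | 54.4% | 69.8% | 15.4 | 16.2 d | 22.5 d | 8.3 d |

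**Step 2: two arms at Day 28** (active v placebo). Placebo has 39% discharged by Day 14 throughout. Active has 53% in A to C. In D it has the placebo discharge hazard and twice the placebo death hazard.

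| Scenario | Mortality | True F(28) | True ratio | 1-KM | 1-KM ratio |
|---|---|---|---|---|---|
| A | 10% v 20% | 74.1% v 57.5% | 1.29 | 80.2% v 66.9% | 1.20 |
| B | 15% v 30% | 72.1% v 54.4% | 1.32 | 81.6% v 69.8% | 1.17 |
| C | 30% v 30% | 64.9% v 54.4% | 1.19 | 87.0% v 69.8% | 1.25 |
| D | 48.2% v 30% | 43.7% v 54.4% | 0.80 | 69.8% v 69.8% | 1.00 |

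A and B are shrunk, C is inflated with equal mortality, and D is hidden.

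**Step 3: the Wilcoxon test.** Simulation with 300 per arm, 1,000 runs and two-sided 5%. The test was run on discharged subjects only, then on everyone with the non-discharged ranked worst.

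| Scenario | Median days, discharged only (active v placebo) | Discharged only: significant for active | Non-discharged ranked worst: significant for active |
|---|---|---|---|
| A | 8.3 v 9.2 | 14.3% | 98.4% |
| B | 7.8 v 8.3 | 6.2% | 98.5% |
| C | 6.0 v 8.3 | 73.7% | 94.9% |
| D | 6.8 v 8.3 | 27.5% | 0% |

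In D the active arm is truly worse. The discharged-only median is nonetheless shorter there, and the test wrongly favours it in 27.5% of runs. With the non-discharged ranked worst, the test goes significantly against it in 50.1%.

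**The case against.** The strongest reply is that the fault is inferred. No text says that deaths are censored on the day of death or that the Wilcoxon test leaves anyone out. The plan does not say whether the median comes from raw days or from the curve. The same Kaplan-Meier command gives the right answer if deaths are kept at risk to Day 28 and follow-up is complete, and the intention-to-treat statement points away from dropping subjects. This stands: the documents show a missing rule, not a proven error. It does not remove the point, because the ordinary use of both named methods gives the wrong quantity.

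A second reply is that reach is small. The plan's rationale for the curves is display in figures, and it takes the risk ratio as its effect measure. This largely stands. A reader might infer that the main efficacy results are in doubt; they are not on this ground, since a death counts as not recovered in the 14-day and 28-day recovery ratios, and mortality is analysed directly. What remains is a named secondary outcome, its test and its curves.

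A third reply is that mortality is assumed, and at 5% the effect is about 2 points. That is also fair, and is why a range is shown.

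Two further inferences fail. One is that the method flatters the drug: in A and B it understates the benefit. The other is that arms are unequally biased only when the drug changes mortality: C contradicts that.

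**Conclusion.** The concern holds as a gap in the plan for one secondary outcome. The final plan names two methods whose ordinary use mishandles deaths and subjects still in hospital, and states no rule that would prevent it. Under that use, alive discharge at Day 28 is overstated by about 2, 4, 9 and 15 points at 5%, 10%, 20% and 30% mortality. These figures rest on constant hazards, 39% discharged by Day 14, and mortality rates that the documents do not supply.

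The effect on the arm comparison has no fixed direction; it depends on both the discharge and the death hazards in each arm. The documents do not support saying that the reported comparison is in fact distorted, or distorted in favour of proxalutamide. The change should be made, but it does not bear on the primary endpoint, the 28-day recovery ratio or mortality.

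**What to change.** In the final plan, sections 2 and 3:

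1. Replace the failure function for alive discharge with the cumulative incidence (Aalen-Johansen) function, with death before discharge as a competing event. Keeping deaths at risk to Day 28 is equivalent only with complete follow-up. The plan allows for 3.5% non-completion, and protocol 5.2 allows missing Day 28 assessments.
2. Take the median and quartiles from that curve, and report a quartile as not reached where the curve does not reach it.
3. Run the Wilcoxon test on all randomised subjects, with deaths and those still in hospital at Day 28 ranked worst. State how subjects lost before Day 28 are handled. Gray's test is an optional alternative.
4. If deaths were already handled this way, one sentence saying so is enough.

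The cost is SAP wording and a re-run on discharge and death dates already held. If deaths had been censored, each arm's discharge curve will be lower and its median longer, while the difference between arms may move either way.

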6.4.3 Reporting Unanticipated Problems to Subjects

Subjects will be informed of any UPs that occur as part of their participation in this trial.

7 Statistical Plan

7.1 *Statistical Methods*

I. General Principles:

- Double-blinded, placebo controlled randomized interventional study with a two-sided type I error rate of 0.05.
- Continuous variables will be expressed as median (interquartile range [IQR]) and categorical variables will be expressed as a number
- 95% confidence intervals will be calculated for the primary outcome
- Group comparisons will be analyzed by the Wilcoxon rank sum test or χ^2 test
- The placebo arm will be used as a reference group when calculating treatment effects
- Differences between rates of clinical improvement will be calculated using unadjusted ordinal logistic regression or Cox proportional hazard models
- Statistical analyses will be conducted using XLSTAT version 2020.5.1 (Addinsoft, Inc.)

II. Statistical Hypotheses:

The primary endpoint is the distribution of clinical assessments on the COVID-19 ordinal scale at day 14. The primary outcome will be analyzed using the Wilcoxon rank sum test.

The Null Hypothesis (H_0) is that the distribution of clinical assessments on the COVID-19 ordinal scale at day 14 among hospitalized COVID-19 subjects treated with Proxalutamide is equal to the distribution of clinical assessments on the COVID-19 ordinal scale at day 14 among hospitalized COVID-19 subjects treated with the Proxalutamide placebo

The Alternative Hypothesis (H_A) is that the distribution of clinical assessments on the COVID-19 ordinal scale at day 14 among hospitalized COVID-19 subjects treated with Proxalutamide is not equal to the distribution of clinical assessments on the COVID-19 ordinal scale at day 14 among hospitalized COVID-19 subjects treated with the Proxalutamide placebo

Mathematically written as:

$$H_0: P(X > Y) = P(Y > X)$$

$$H_A: P(X > Y) \neq P(Y > X)$$

Where X and Y are randomly selected clinical assessments from the two treatment arms in the study.

III. Primary Efficacy Analysis:

- The non-parametric Wilcoxon rank sum test (Mann Whitney U) will be used to assess the primary end point.
- P-values <0.05 will be considered significant. All statistical analysis will be based on the intent-to-treat (ITT) population. All missing data will be described.

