
The Null Hypothesis (H0) is that the distribution of clinical assessments on the COVID-19 ordinal scale at day 14 among hospitalized COVID-19 subjects treated with Proxalutamide is equal to the distribution of clinical assessments on the COVID-19 ordinal scale at day 14 among hospitalized COVID-19 subjects treated with the Proxalutamide placebo
	
The null hypothesis applied to the primary endpoint Overall Recovery Ratio is that there is no association between the recovery risk rates of the study arms and the type of treatment (proxalutamide or placebo) in the hospitalized patients with COVID-19
	
Since the primary outcome was refined with a clear efficacy endpoint, defined as a binary measure, the null hypothesis was rephrased to be in line with the chi-square test.

The Alternative Hypothesis (HA) is that the distribution of clinical assessments on the COVID-19 ordinal scale at day 14 among hospitalized COVID-19 subjects treated with Proxalutamide is not equal to the distribution of clinical assessments on the COVID-19 ordinal scale at day 14 among hospitalized COVID-19 subjects treated with the Proxalutamide placebo
	
The alternative hypothesis applied to the primary endpoint Overall Recovery Ratio is that there is an association between the recovery risk rates of the study arms and the type of treatment (proxalutamide or placebo) in the hospitalized patients with COVID-19, meaning that the experimental treatment may affect the Overall Recovery Ratio.
	
The primary outcome was refined with a clear efficacy endpoint, defined as a binary measure the alternative hypothesis was rephrased to be in line with the chi-square test.

5. Primary analysis efficacy

As proposed in the final protocol	Done in the final statistical Plan	Rationale

The non-parametric Wilcoxon rank sum test (Mann Whitney U) will be used to assess the primary end point. P-values <0.05 will be considered significant. All statistical analysis will be based on the intent-to-treat (ITT) population. All missing data will be described.
	
The non-parametric Wilcoxon rank sum test was used to assess some of the secondary outcomes described above.
 
The intention-to-treat protocol was performed in the final analysis. Missing data was reported.
	
The primary outcome was refined with a clear efficacy endpoint, defined as a binary measure, and thus, Wilcoxon Rank Sum test was not appropriate for such type of variable.

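### At manuscript stage the primary test moved from Wilcoxon on the Day-14 8-point score to chi-square on scores 1–2, yet the plan calls the outcome unchanged and its testing maintained

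*Combined protocol and SAP*

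**What the plan says.** **Final protocol, section 7.1 (II and III).** The primary endpoint is the Day-14 distribution over the 8-point scale, and the test is named: "The primary outcome will be analyzed using the Wilcoxon rank sum test". The null hypothesis is P(X > Y) = P(Y > X), two-sided at 5%.

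**Final Statistical Plan.**
- Section 4 makes the 14-day recovery ratio the primary efficacy endpoint: "This effect measure was obtained after dichotomization of the COVID-19 ordinal scale for scores 2 and 1". On the hypotheses, its rationale column says "the null hypothesis was rephrased to be in line with the chi-square test"; the alternative is treated the same way.
- Section 5 gives Wilcoxon a new role, "The non-parametric Wilcoxon rank sum test was used to assess some of the secondary outcomes described above", because for a binary endpoint the "Wilcoxon Rank Sum test was not appropriate for such type of variable".
- Section 3 reports confidence intervals in the results tables "for the primary endpoint Overall Recovery Ratio), along with the P value".
- Section 1 marks the ordinal primary outcome 'No change', on the ground that the Day-14 distribution includes every score from 1 to 8. The next row adds the recovery ratio as the effect measure.
- The rationale column of section 3 says "The primary hypothesis testing previously stated was maintained".
- The rationale column of section 4 adds: "Although the distribution is still presented graphically, and tested for statistical significance". It does not name the test.

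The introduction and the closing note both date the changes to the writing of the manuscript.

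**The concern.** A chi-square test at a cut fixed in advance is a valid 5% test. The difficulty is that the test deciding the trial was chosen at manuscript stage, and the plan's own labels invite the reader to take its p-value as the prespecified primary result. If the two tests can reach different decisions on the same data, the choice between them can decide whether the trial is called positive.

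The estimand also changes. A comparison of scores 1–2 with 3–8 does not register Day-14 movement within 3–8, such as from supplemental oxygen to ventilation or death. Mortality at 28 days is reported separately, which covers part of that loss.

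**Working it through.** **1. The two texts side by side**

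| Element | Final protocol 7.1 | Final Statistical Plan |
|---|---|---|
| Primary endpoint | Day-14 8-point distribution | 14-day recovery, scores 1–2 (section 4) |
| Hypotheses | P(X > Y) = P(Y > X) | No association between arm and recovery (section 4) |
| Deciding test | Wilcoxon | Chi-square (sections 3–5) |
| Role of Wilcoxon | Primary | Some secondary outcomes (section 5) |
| Label on the outcome | – | 'No change' (section 1) |
| Label on the testing | – | Maintained (section 3) |

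The last two rows conflict with those above them. All the entries in the right-hand column stand in the plan's own final or rationale columns, so this is a contradiction within the current plan, not a log describing superseded text.

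**2. Timing.** Some analyses existed when the plan was written: section 2 says lower age cut-offs gave nothing worth reporting, and section 3 reports the proportional-hazards check as done. Neither shows that those analyses came before the choice of cut. The plan does not say when the cut was fixed relative to unblinding.

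**3. The plan's sample size** (protocol 7.2: odds ratio 2, 90% power, two-sided 5%, 3.5% dropout). The ordinal formula is N = 12(z_α/2 + z_β)² / [λ²(1 − Σp³)] with λ = ln 2, so N = 262.4 / (1 − Σp³).
- The stated 294 per cohort leaves 294 × 0.965 = 283.7 evaluable, which implies Σp³ = 1 − 262.4/283.7 ≈ 0.075. The category probabilities come from an outside protocol's scenario 4 and are not in the documents, so 294 cannot be confirmed. It is plausible for a multi-category outcome: Σp³ from 0.016 to 0.15 gives 277 to 320 after dropout.
- For the binary endpoint, odds 0.39/0.61 × 2 give 56.1% recovery. The mean of 39% and 56.1% gives Σp³ = 0.252, so N = 351, or 364 after dropout. The usual two-proportion formula gives 177 per arm, 354 in all, or 354/0.965 = 367. Thus 294 fits the ordinal test, not the binary one.

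**4. Simulation.** 400,000 trials per scenario; tie-corrected Wilcoxon and uncorrected 2×2 chi-square, each at two-sided 5%. Evaluable per arm: 147 × 0.965 ≈ 142 for one cohort, 294 × 0.965 ≈ 284 pooled. Placebo has 39% at scores 1–2 (the plan's figure). Assumed placebo splits over scores 1 to 8, in %:
- A: 20/19/4/8/20/8/11/10
- B: 10/29/3/5/15/10/18/10
- C: 30/9/8/12/18/6/9/8

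No effect (A/B/C):

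| | 142 per arm | 284 per arm |
|---|---|---|
| Wilcoxon rejects | 0.0501/0.0500/0.0500 | 0.0501/0.0495/0.0499 |
| Chi-square rejects | 0.0495/0.0486/0.0490 | 0.0513/0.0508/0.0512 |
| Decisions differ | 0.0481/0.0472/0.0473 | 0.0495/0.0473/0.0480 |
| Chi-square only | 0.0238/0.0229/0.0232 | 0.0253/0.0243/0.0247 |

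For split A at 142 per arm, 0.0238/0.0495 = 48% of chi-square rejections are not Wilcoxon rejections. Across all six cells the range is 47–49%.

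With an effect, proportional odds (A/B/C):

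| | Wilcoxon | Chi-square | Decisions differ |
|---|---|---|---|
| OR 2, 142 per arm | 0.909/0.905/0.902 | 0.828/0.826/0.828 | 0.107/0.105/0.100 |
| OR 2, 284 per arm | 0.996/0.996/0.996 | 0.983/0.984/0.984 | 0.014/0.014/0.013 |
| 39% to 53%, 142 per arm | 0.770/0.765/0.762 | 0.658/0.658/0.659 | not tabulated |
| 39% to 53%, 284 per arm | 0.969/0.967/0.966 | 0.917/0.916/0.916 | not tabulated |

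The 39% to 53% rows use the 14-point difference restated in section 6 of the Final Statistical Plan. That corresponds to an odds ratio of (0.53/0.47)/(0.39/0.61) = 1.76, not 2.

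**The case against.** **The change is disclosed.** The recovery ratio appears in the row straight after 'No change', and sections 4 and 5 set out the dichotomisation, the new hypotheses and the new place of Wilcoxon. This stands: the fault is contradictory labelling and late choice, not concealment. It also makes 'No change' the weaker of the two labels, since that row concerns the outcome measure. The claim that testing was maintained is the harder one to defend against section 5.

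**Maintained has a partial reading.** It sits in the general group-comparison row, where the protocol allowed Wilcoxon or chi-square, and section 4 says the distribution is still tested. So the replacement concerns the primary role only. But protocol 7.1 names Wilcoxon specifically for the primary endpoint, and the surviving test of the distribution has neither a name nor primary status.

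**The cut was not invented late.** Scores 1–2 define recovery in protocol 3.1 and in 5.1 III item 2. Both uses lie outside the primary outcome, and 5.1 II counts scores 1–3 as recovery, so another cut was available. The authors say they had always intended the recovery ratio, and concede in the same place that the protocol did not set it out clearly.

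**The switch does not favour the drug on average.** True under proportional odds: chi-square is the less powerful test. That does not make it the prespecified test. The two also agree in about 95% of null trials, so the risk is best described by the conditional 47–49%.

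**An effect measure was needed.** Yes, but protocol 7.1 already lists ordinal logistic regression and 7.2 is written in odds ratios, so one was available without changing the test.

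**Conclusion.** The concern holds. The deciding primary test was changed at manuscript stage, and the plan says in two places that nothing of the kind happened. The central harm is that the primary p-value does not come from the prespecified test.

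Under no effect each test holds about 5%, decisions differ in 4.7–5.0% of trials, and 47–49% of chi-square-significant trials are not significant by Wilcoxon. At an odds ratio of 2, one cohort loses 7–8 points of power (90–91% to 83%) and decisions differ in 10–11% of trials. With cohorts pooled the loss is about one point and power is a minor matter.

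These figures rest on 39% placebo recovery (taken by the plan from a Day-15 figure), proportional odds and three assumed splits. The findings on the text need none of these assumptions. No document shows that the choice was driven by results by arm.

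**What to change.** - Restore Wilcoxon on the Day-14 8-point score as the single primary test, with the proportional-odds common odds ratio and its 95% confidence interval as the effect measure.
- Report the 14-day recovery ratio and its chi-square p-value as supportive, labelled as defined at manuscript stage.
- Reconcile sections 1 and 3–5 of the Final Statistical Plan: withdraw the unchanged and maintained labels wherever they cover the replaced test, and name the test applied to the distribution in section 4.
- State when the scores 1–2 cut was fixed relative to unblinding.
- State whether the primary test is per cohort, as protocol 7.2 is sized, or pooled, as the overall ratio implies.

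The cost is wording plus one re-run on existing data. The drawback is a headline odds ratio in place of a risk ratio.

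This does not by itself secure 5%. Protocol 7.4 plans an efficacy look at half the recruitment. If that look and the final analysis are each tested at an unadjusted 5%, the overall null rate in the same simulation is 8.2–8.4% with either test. The alpha for that look has to be settled separately.
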